12 SOURCE DOCUMENTS AND ACCESS TO SOURCE DATA

Source documents will include internet forms self-completed by participants directly entered into a RedCAP database.

This protocol is based on self-report.

This internet-based protocol is meant to enable a large number of participants to be recruited, quickly as well as maintain the safety of the research staff. In person visits, create a public health

Participants will be asked to provide consent to obtain medical records from their healthcare provider or public health official, if there is the need to verify outcomes – for SARS-CoV-2 test results or hospitalizations.

13 QUALITY CONTROL AND QUALITY ASSURANCE

Study medications will be commercially procured U.S. FDA-approved hydroxychloroquine or under ANDA #210959 following Good Manufacturing Practice.

14 ETHICS/PROTECTION OF HUMAN SUBJECTS

14.1 Ethical Standard

This study is to be conducted according to US and international standards of Good Clinical Practice (International Conference on Harmonization guidelines), Declaration of Helsinki, and International Ethical Guidelines for Biomedical Research Involving Human Subjects, applicable U.S. government regulations and institutional research policies and procedures. All investigators must have received human subject protection and GCP training prior to human subject involvement.

14.2 Institutional Review Board

Prior to the initiation of the study, the protocol, all informed consent forms and the participant Information materials will be submitted to and approved by the single IRB of record. Likewise, any future amendments to the study protocol will be submitted and approved by the IRB before implementation. This protocol and any amendments will undergo review and approval by the Human Subjects Board at the University of Minnesota under DHHS Assurance FWA00000312.

14.3 Informed Consent Process

- Written informed consent will be obtained via an English-language, internet-based web form. If potential participants have questions, they may contact [contact] to reach a study staff member to answer their questions about research, either via email or a phone call.
- After completion of reading the form, participants will be assessed for comprehension, querying:
 - Concept of Randomization to hydroxychloroquine or vitamin placebo
 - Whether hydroxychloroquine is known to be effective in preventing disease
 - Duration of the study? (14 days)
 - Duration of taking the study medicine (5 days)
 - When follow up surveys will be sent (Days 1, 3, 5, 10 and 14)
 - If hydroxychloroquine can be shared? (No)

14.3.1 Informed Consent/Assent Process (in Case of a Minor)

- Persons under 18 years of age are not eligible to participate. COVID19 has negligible mortality in children <10 years, and rate of progression to symptomatic disease may likely be different. Furthermore, pediatric dosing is weight based, making remote administration more complicated with fixed dose 200mg tablets.

14.4 Exclusion of Women, Minorities, and Children

- Persons under 18 years of age are not eligible to participate. COVID19 has 0% mortality in children and young adults.
- Non-English speaking adults are not eligible as the webpage and consents will only be available in English.

14.5 Subject Confidentiality

- Interaction will be via internet-based RedCAP ECRFs conforming to required U.S. privacy and server security standards.
- Clinical data will be entered into a study specific database by designated staff on a regular basis from completed electronic Case Record Forms (eCRF). Access to database will be given to authorized personnel only (members of the immediate study team). eCRF and trial documents will be kept in a secure database.
- Documentation, data and all other information generated will be held in strict confidence. No information concerning the study or the data will be released to any unauthorized third party, without prior written approval of the participant except as necessary for monitoring by the IRB or public health authorities
- No participant identifying information will be disclosed in any publication or at any conference activities arising from the study.

14.6 Future Use of Stored Specimens

- No specimens are to be stored for future research.

15 DATA HANDLING AND RECORD KEEPING

15.1 Data Management Responsibilities

Investigators will maintain a REDCAP database of study records.

Survey forms will be self-completed by study participants.

15.2 Data Capture Methods

- Data will be obtained via internet-based REDCAP forms.

15.3 Types of Data

- Participants will be asked to provide data regarding COVID19 exposure timing and location. They will also be asked to provide ongoing symptom reports during the follow-up period.

15.4 Timing/Reports

- An enrollment progress report will be generated monthly
 - Participants Enrolled
 - Participants on study
 - Participants completed the study
 - Lost to Follow Up
 - Cumulative COVID19 (pooled, both arms)
 - Cumulative Hospitalizations (pooled, both arms)
- A data safety monitoring board (DSMB) will review data after every 100 participants complete 14 days of follow-up.
- De-identified data will be shared with the research team members for analysis.

15.5 Study Records Retention

- No paper documents will be retained or stored.
- Digital records will be kept in a secure server setting.

15.6 Protocol Deviations

Protocol violations will be reported to the IRB of record.

16 PUBLICATION POLICY

Publication will be expeditiously made with a full, de-identified data made available.

[figure not shown]

- d. The primary outcome will be presented by subgroups formed by COVID test results (confirmed positive vs. other), age groups (18-35, 36-50, > 50), sex, and days from exposure onset to entry. These are apriori subgroups defined in the Version 1.0 of the protocol.
- e. Medication adherence is captured on study day 5. Another subgroup of interest is comparing the treatment groups for change in symptom severity score after day 5 by adherence reported at day 5 ($\leq 75\%$ versus $> 75\%$).

II. Secondary outcomes

- a. Secondary outcomes for incidence will be presented as proportions and compared between the treatment groups with Fisher’s Exact tests.
- b. Symptom severity scores were recorded with the online participant surveys at days 3, 5, 10 and 14 only for those who responded “yes” to “Any symptoms experienced”.

- i. Visual analog scale (0-10) for “overall symptom severity” is collected via a digital slider bar, which is marked with “0 = no symptoms”; 5 (placed in the middle); and “10 = severe symptoms”

Severity of overall symptoms?

Please click to move the slider, even if your symptoms are a 5

* must provide value

0 = No symptoms 5 10 = Most severe

- ii. For those who responded “no” to “Any symptoms experienced” the symptom severity score for that visit is assigned as zero.
- iii. For those hospitalized or with deaths, their symptom severity was scored as 10 if they did not respond to the visit survey.
- iv. Analysis is by Kruskal Wallis tests among those with symptoms at day 14.

Clarifications (24 May 2020):

- Participants with missing outcome data are still included in the denominator, as the trial is performed as an intent to treat analysis.
- Sensitivity analyses were performed excluding participants with missing data from the denominator as well as including participants with missing data as events.

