3.2.2 Secondary Outcome Measures

- Incidence of hospitalization or death
- Incidence of confirmed SARS-CoV-2 detection
- Incidence of symptoms compatible with COVID-19 (possible disease)
- Incidence of all-cause study medicine discontinuation or withdrawal
- Incidence of adverse reactions
- Symptom severity on day 5 or 14 via visual analog scale
- Ordinal Scale of COVID-19 Disease Severity at day 14 (among those who are symptomatic at trial entry)
 - Illness without hospitalization
 - Hospitalization (or post-hospital discharge)
 - Hospitalization with ICU stay or Death

Assessment of outcome measures will be primarily by self-report. As necessary, COVID19 disease will be verified from public health records, medical records, or death certificates. The primary endpoints are different for the two cohorts (those who are asymptomatic with known exposure; or those who are symptomatic at trial entry), and analyses will be done separately for the two cohorts.

The primary analysis will use PCR+ confirmed disease. However if the absence of sufficient testing supplies continues then outpatients will not be offered SARS-CoV-2 testing unless they are sick enough to be hospitalized. In that case an alternate a priori planned analysis will define incident COVID19 disease as a composite of SARS-CoV-2 PCR+ confirmed result OR symptomatic disease (i.e. possible) COVID-19 in those without testing.

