7.2 Enrollment/Baseline

Randomization (Day 0)

- Participants will be randomized by a computer-generated algorithm using a permuted block randomization sequence.
- Randomization will be stratified by symptomatic vs. asymptomatic status at baseline.
- Investigational pharmacy will dispense the masked study medicine
- Study personnel will then FedEx study medicine to the participant
- Participant will be sent an email to expect medication to arrive by 10:30am

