7.3 Follow-up

Day 1 Virtual visit

- Verify receipt of study medicine
- Clinical status check-in
 - Participant starts study medicine (4 tabs), then 3 tabs in 6-8 hours, then 3 tabs daily.
- Query for SARS-CoV-2 testing
- Query for symptom status (0-10 visual analog scale of symptom severity)
- Query for hospitalization or SAEs
- Query for medication-related side effects / AEs

Day 3 Virtual visit

- Query for symptom status (0-10 visual analog scale of symptom severity)
- Query for hospitalization or SAEs
- Query for medication-related side effects / AEs

Day 5 Virtual visit

- Query for symptom status (0-10 visual analog scale of symptom severity)
- Assessment of adherence by self-report
- Completion of study medicine, which has a ~7 day half-life
- Query for study medicine side effects since enrollment
- Query for SARS-CoV-2 testing
- Query for hospitalization or SAEs

Day 10 Virtual visit

- Query for symptom status (0-10 visual analog scale of symptom severity)
- Query for SARS-CoV-2 testing

- Query for SARS-CoV-2 testing
- Query for hospitalization or SAEs

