9.2 Methods and Timing for Assessing, Recording, and Analyzing Safety Parameters

9.2.1 Adverse Events

Hydroxychloroquine has an excellent safety track record, being first FDA-approved in 1955. Adverse events will not be captured, unless they result in hospitalization. See Serious Adverse Events below.

Expected adverse events would include normal events within the general population as well COVID19-related disease events which may include need for hospitalization, pneumonia, respiratory failure, sepsis, and death.

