11.4 Final Analysis Plan

Primary outcome analyses (intention to treat):

Asymptomatic Cohort Primary Analysis:

Those with asymptomatic exposure: Incidence of COVID 19 disease by day 14 will be assessed via Fisher's Exact Test.

Symptomatic Cohort Primary Analysis:

Those with symptomatic disease at study entry: For a summary metric of the change in symptom severity over 14 days, a longitudinal change over time repeated measures mixed-regression model will estimate the treatment effect by study arm. Subjects without symptoms are coded as a zero severity. Persons hospitalized or dead are coded as 10 severity.

Participants who become symptomatic with COVID19 on Day 1 before receiving the study medicine will be described with the symptomatic cohort.

Secondary Analyses:

For the asymptomatic with exposure cohort, the primary analysis (intention to treat) will be repeated for participants who received at least one dose of the study medicine.

- Secondary endpoints will be assessed via Fisher's Exact test and median (with interquartile ranges) as appropriate.
- Those with symptomatic disease at study entry: Proportional odds models will be used to assess the ordinal scale for disease severity at day 14 (illness without hospitalization, hospitalization without ICU stay or death, or hospitalization with ICU stay or death).
- Severity of overall symptoms at Day 0, 1, 5, and 14 is recorded on a 0-10 visual analog scale. Severity of symptoms at Day 5 will be compared first as a categorical analysis (no symptoms vs. symptoms) via Fisher's Exact Chi Square.
 - Second among those with symptoms, the 0-10 visual analog scale severity data will be compared via independent two-sample *t* test. If data are non-normally distributed, then data will be compared via Mann-Whitney U by study arm.

A priori subgroup analyses will include assessment by:

- Confirmed SARS-CoV-2 disease or disease exposure
- Healthcare worker vs. Household contact
- Days from Exposure
- Decile of age
- Sex as a biological variable
- Censored subjects, who became symptomatic before receipt of the first dose of study medicine on D#1, will be separately analyzed and reported.

Handling of withdrawn subjects.

If there is a large lost to follow up / study discontinuation rate, then the primary endpoint for the asymptomatic cohort would have a secondary analysis to assess incidence as a 3-category analysis of: i) no disease, ii) incident disease, or iii) unknown.

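### Incidence of adverse reactions has no safety analysis set; read as written, the main side-effect table counts undosed and non-answering participants as reaction-free, which dilutes absolute incidence

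*Combined protocol and SAP*

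**What the plan says.** Protocol 3.2.2 lists "Incidence of adverse reactions" among the secondary outcomes, without a denominator. SAP II.a covers outcomes of this type: "Secondary outcomes for incidence will be presented as proportions and compared between the treatment groups", using Fisher's exact test. It names no analysis set.

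The SAP Clarifications (24 May 2020) give the only denominator rule for main analyses: "Participants with missing outcome data are still included in the denominator, as the trial is performed as an intent to treat analysis". The next bullet adds: "Sensitivity analyses were performed excluding participants with missing data from the denominator as well as including participants with missing data as events". Neither bullet says which outcomes it covers.

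The only dose-based set is in protocol 11.4. For the asymptomatic cohort, "the primary analysis (intention to treat) will be repeated for participants who received at least one dose of the study medicine". It is not used for any safety outcome.

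On data collection, protocol 7.3 lists "Query for medication-related side effects / AEs" at Days 1 and 3. The Day 5 list (7.3) and the Day 14 list (7.4) ask about side effects over the whole time since enrolment. Protocol 9.2.1, however, says: "Adverse events will not be captured, unless they result in hospitalization".

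**The concern.** A side effect can enter the numerator only if the participant took study medicine and answered a survey that asks about side effects. The denominator, on the plain reading of the Clarifications, is everyone randomised. The two groups differ by design. Randomisation is on Day 0, and only afterwards is the medicine posted (protocol 7.2: "Study personnel will then FedEx study medicine to the participant"). Protocol 11.4 and SAP I.c both expect some participants to fall ill before receiving it.

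Counting missing participants as events is a separate sensitivity analysis, so the main analysis must count them as non-events. For an efficacy outcome, keeping all randomised participants protects the comparison. For a side-effect rate, it adds people who could not have had a drug reaction, or in whom none could be observed, and calls them reaction-free.

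What is at stake is the absolute side-effect rate, which matters for a drug given to healthy exposed people. Below the level of hospitalisation, this is the only planned comparison specific to side effects. Discontinuation or withdrawal is also compared between arms, but for all causes together.

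**Working it through.** **Plan's own figure.** The documents state no adverse-reaction rate, no number dosed and no number answering, so there is nothing to reproduce for this outcome. The sample size behind the 750 per arm (621 per arm for 10% versus 5%, two-sided 0.05, 90% power) does reproduce with the continuity-corrected formula, but it does not bear on this point.

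**Inputs**
- N = 750 per arm and loss to follow-up of up to 20%: protocol 11.2.
- m, the share of an arm that is undosed or answered no side-effect query: not given. Assumed range 5% to 20%.
- p, the true incidence among dosed participants who answered: not given. Assumed 40% versus 20% for the main illustration, with 30% versus 15% and 10% versus 5% as alternatives.

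**Formula.** If the m share counts as reaction-free, and p is the rate among the rest:

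reported incidence = p × (1 - m)

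**Equal m in both arms, true rates 40% versus 20% (difference 20 points, relative risk 2.0)**

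| m | Active | Placebo | Difference | Relative risk |
|---|---|---|---|---|
| 5% | 0.40 × 0.95 = 38% | 0.20 × 0.95 = 19% | 19 points | 2.0 |
| 10% | 0.40 × 0.90 = 36% | 0.20 × 0.90 = 18% | 18 points | 2.0 |
| 15% | 0.40 × 0.85 = 34% | 0.20 × 0.85 = 17% | 17 points | 2.0 |
| 20% | 0.40 × 0.80 = 32% | 0.20 × 0.80 = 16% | 16 points | 2.0 |

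The relative loss does not depend on p. At m = 20%, true rates of 30% versus 15% are reported as 24% versus 12% (12 points instead of 15), and 10% versus 5% as 8% versus 4% (4 points instead of 5).

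**Effect on the test.** Take 10% versus 5% with m = 20%. Among 600 observed per arm there are 60 and 30 events, Fisher p = 0.0014. With the same events over 750 per arm, p = 0.0015. Approximate power is 0.909 and 0.904 respectively. The test hardly moves.

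**Unequal m, true rates 40% versus 20%**
- 20% active, 10% placebo: 0.40 × 0.80 = 32% versus 0.20 × 0.90 = 18%. Difference 14 points, relative risk 1.78.
- 10% active, 20% placebo: 0.40 × 0.90 = 36% versus 0.20 × 0.80 = 16%. Difference 20 points, relative risk 2.25.

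The first pulls the contrast towards no effect. The second leaves the difference at its true value and raises the relative risk.

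**What the existing sensitivity analyses would do.** Excluding missing participants, if applied here, removes those who never answered. It does not remove someone who took no tablet and reported no side effects, because that person's outcome is not missing. Counting missing as events at m = 20% gives (240 + 150)/750 = 52% versus (120 + 150)/750 = 36%.

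**Why 20% is an upper illustration.** Side effects are asked about on Days 1, 3, 5 and 14, and two of those queries look back to enrolment. A participant lost by Day 14 may already have answered. Also, m counts each person once: if those who never start are mostly those who never answer, the two shares overlap and should not be multiplied as if independent.

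**The case against.** The strongest objection is that the Clarifications already supply the remedy. If the all-randomised rule reaches adverse reactions, so does the next bullet, and one of its analyses excludes participants with missing data. This stands in part. It would deal with non-responders, but its scope is not stated, it leaves in undosed participants who report no side effects, and the diluted figure remains the main result.

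Second, no sentence applies the denominator rule to adverse reactions, and protocol 5.3.3 gives another secondary endpoint its own rule (withdrawals count as failures of medication completion). This stands: the application is an inference. The alternative reading, that no denominator is specified at all, calls for the same correction.

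Third, a reader might infer that the plan makes the drug look closer to placebo. The documents do not support that as a general statement. With equal m the relative risk is unchanged and the test nearly so; with unequal m the direction depends on which arm has more undosed or silent participants, which is unknown.

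Fourth, a reader might take the 20% planning loss as the share never observed for side effects. It is a ceiling on loss to follow-up, not an estimate of people who missed all four queries.

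Finally, if side effects themselves cause silence, an analysis of responders also understates the rate. This stands, and is why the fix includes a missing-as-events bound.

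**Conclusion.** The point holds for absolute incidence. No safety set is defined, and following the plan as written counts undosed and non-answering participants as reaction-free in the main table. The understatement is a factor of (1 - m): 5% to 20% in relative terms for an assumed m of 5% to 20%, probably nearer the lower end given four queries. With equal m the risk difference falls in the same proportion. No direction can be claimed for the comparison between arms.

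This rests on two assumptions: that the Clarifications' denominator rule extends to this outcome, as its general wording suggests, and that the size of m, which the documents do not give, lies in the range shown. The primary efficacy analyses are unaffected. The change should be made because the side-effect rate will be read as an absolute risk.

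**What to change.** In SAP II.a and protocol 11.4:

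- Make the main analysis of adverse reactions the participants who took at least one dose and answered at least one side-effect query after that dose.
- Report the numbers randomised, dosed and answering, by arm. Adherence is self-reported at Day 5 (protocol 6.5), so also show how many have unknown dosing status.
- State that the missing-as-events sensitivity analysis applies to this outcome among dosed participants, as a bound in case side effects cause non-response.
- Keep the all-randomised denominator as a secondary display.
- Reconcile protocol 9.2.1, which rules out capturing adverse events short of hospitalisation, with 3.2.2, 7.3 and 7.4, which list and query them.

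The cost is a few sentences and one extra table. The side-effect answers are already collected, and the at-least-one-dose analysis in 11.4 already needs the dosing information. The downsides are a less favourable reported side-effect rate and a main set that is not strictly randomised, which is why the all-randomised display stays alongside it.

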3.2 Study Outcome Measures

3.2.1 Primary Outcome Measures

Asymptomatic Cohort

- Incidence of COVID-19 disease within 14 days (among those asymptomatic at baseline)

Symptomatic Cohort

- Change in symptom severity score (visual analog scale 0-10) over 14 days

[figure not shown]

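### Protocol 11.4 scores every hospitalised participant 10 on the symptom scale; SAP II.b.iii does so only when the visit survey went unanswered, and neither text says which rule governs which analysis

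*Combined protocol and SAP*

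**What the plan says.** Protocol 3.2.1 gives the symptomatic cohort's primary outcome as "Change in symptom severity score (visual analog scale 0-10) over 14 days". Protocol 11.4, under Symptomatic Cohort Primary Analysis, states the model ("a longitudinal change over time repeated measures mixed-regression model will estimate the treatment effect by study arm") and the coding: participants without symptoms score zero, and "Persons hospitalized or dead are coded as 10 severity". Nothing there depends on whether a survey was returned.

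The SAP handles the same scale under II, Secondary outcomes. Item II.b.ii covers people who answer the survey and report no symptoms: "the symptom severity score for that visit is assigned as zero". Item II.b.iii says of participants who were hospitalised or died that "their symptom severity was scored as 10 if they did not respond to the visit survey". Item II.b.iv then names the test: "Analysis is by Kruskal Wallis tests among those with symptoms at day 14".

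The SAP also uses the score in item I.e, a subgroup look "comparing the treatment groups for change in symptom severity score after day 5 by adherence reported at day 5". It does not restate the mixed model or any coding for the symptomatic cohort's primary analysis. The clarifications of 24 May 2020 deal with missing outcome data and the denominator, and do not touch this rule.

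**The concern.** The two sentences define different variables. In 11.4, hospitalisation itself is the worst state on the scale. In II.b.iii, 10 is a fill-in value for a hospitalised person whose survey is missing. Two equally ill inpatients can then score 10 and 4 because one of them opened the survey and the other did not.

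The surveys are web forms that participants complete themselves (protocol 7 and 15.1), so an inpatient may well be able to answer. If inpatients who answer tend to be the less ill ones, which is plausible but not stated in the documents, response is related to severity. If response among inpatients differs between arms, the coding alone can create or hide a difference.

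At stake is a scale that is the primary outcome in one cohort and a secondary outcome (severity at days 5 and 14) in the trial as a whole. An analyst who follows the SAP and one who follows the protocol would build different data sets from the same records.

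**Working it through.** **Step 1. The two rules side by side, for one participant at one visit**

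| Participant at the visit | Protocol 11.4 | SAP II.b |
|---|---|---|
| Hospitalised, survey not answered | 10 | 10 |
| Hospitalised, answers, moves slider to 4 | 10 | 4 |
| Hospitalised, answers no to any symptoms | 10 | 0 |
| Dead | 10 | 10 (cannot answer) |

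The rules part only for living inpatients who answer.

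**Step 2. What the documents provide for sizing.** There is no figure of the plan's own to reproduce: neither document gives a standard deviation, an expected difference or a sample size for the symptom scale. The inputs are:
- h, the share hospitalised. Protocol 11.2 assumes 8% + 2% = 10% in the symptomatic placebo group, or 75 of 750.
- r, the share of inpatients who answer. Not given; taken from 0 to 1.
- s, the mean self-rating of inpatients who answer. Not given; shown for 0 to 8.

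**Step 3. Shift in one arm's mean at one visit.** Under 11.4 inpatients average 10. Under II.b.iii they average 10(1 − r) + s·r. Going from the first rule to the second lowers the arm mean by h × r × (10 − s). With h = 0.10, and treating everyone ever hospitalised as an inpatient at that visit:

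| s | r = 0 | r = 0.5 | r = 1 |
|---|---|---|---|
| 0 | 0 | 0.50 | 1.00 |
| 4 | 0 | 0.30 | 0.60 |
| 5 | 0 | 0.25 | 0.50 |
| 6 | 0 | 0.20 | 0.40 |
| 8 | 0 | 0.10 | 0.20 |

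**Step 4. Contribution to the difference between arms.** Assume 10% v 5% hospitalised (the 5% is an assumed halving) and equal r and s in both arms. Under 11.4 inpatients contribute (0.10 − 0.05) × 10 = 0.50 points. Under II.b.iii they contribute 0.05 × [10(1 − r) + s·r]:
- r = 0.5, s = 5: 0.05 × 7.5 = 0.375
- r = 0.5, s = 6: 0.05 × 8 = 0.40
- r = 1, s = 6: 0.05 × 6 = 0.30
- r = 1, s = 4: 0.05 × 4 = 0.20

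**Step 5. Unequal response, equal hospitalisation.** With 10% hospitalised in both arms and response differing by 20 percentage points, the coding alone produces 0.10 × 0.20 × (10 − s): 0.12 points at s = 4, 0.08 at s = 6 and 0.04 at s = 8. Under 11.4 it is zero.

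**Step 6. The prophylaxis cohort.** Assume a 10% attack rate and 10% progression among those who fall ill. Then h = 0.10 × 0.10 = 1%, about 7.5 of 750, and at r = 0.5 and s = 5 the shift is 0.01 × 0.5 × 5 = 0.025 points.

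**Step 7. The SAP's own test.** Item II.b.iv is a rank test restricted to those with symptoms at day 14, so a shift in means does not measure its effect. There is a separate consequence: an inpatient who answers no to symptoms scores 0 and may leave the analysed set, whereas 11.4 would score that person 10.

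**The case against.** The strongest reply is that the two rules belong to different analyses. The coding in 11.4 sits inside the symptomatic primary model. Item II.b.iii sits under Secondary outcomes and leads into a rank test at day 14. The SAP's version table lists only incidence of COVID-19 as primary endpoint, its heading I names only the prophylaxis study, and I.c calls the other cohort a companion. A reader might infer that the SAP has replaced the coding in the symptomatic primary model. The documents do not support that: the SAP never mentions the model, and a shared scale does not prove a shared derivation. Nor do they exclude it. The SAP carries the title of the whole trial, subgroup item I.d splits by COVID test result, and I.e uses the change in severity score. The scope is therefore unclear.

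A second reply is that keeping an observed self-rating and filling in the worst value only when it is missing is a defensible way to score a symptom scale, since hospitalisation and death are counted separately elsewhere. That stands as a matter of principle. But it is not the coding that the protocol specified, and the SAP departs from it without comment.

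A third reply concerns size, and it largely stands. A reader might take from step 4 that the treatment effect is attenuated by 25% (0.125 of 0.50). That is the loss in one component, at one visit, under assumed response and scores. It is not an estimate for the endpoint or for the rank test.

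**Conclusion.** The inconsistency is firm. For a living hospitalised participant who answers the survey, the protocol gives 10 and the SAP gives the self-rating or 0. On the SAP's only rule for hospitalisation, the severity score depends on who responds. It is also unresolved which rule governs which analysis; the documents do not establish that the symptomatic primary model has been changed.

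The size is not determined by the documents. It is nil if no inpatient answers. In the symptomatic cohort it is 0.25 points on an arm mean at a single visit under h = 10%, r = 0.5 and s = 5, on the assumption that all those hospitalised are inpatients at that visit. It is less when averaged over visits to day 14, because people are not hospitalised throughout, and about a tenth of that in the prophylaxis cohort under the assumptions of step 6. The point deserves correction because it touches a primary-outcome variable and costs little to settle, not because a large bias has been shown.

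**What to change.** Amend SAP II.b.iii so that hospitalised or dead participants score 10 whether or not the survey was answered, wherever the severity score is analysed, and say explicitly that this coding applies to the symptomatic cohort's primary mixed model. State which visits it covers: those during the stay, those after discharge, and those after death. Protocol 11.4 does not say. Protocol 4.4 provides for collecting the hospitalisation date; if the rule is limited to visits during the stay, confirm that the discharge date is available too. Report the analysis with observed self-ratings for hospitalised responders as a sensitivity analysis.

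The cost is a few lines in the SAP and one extra analysis run. The drawback is that self-ratings given by hospitalised responders are overridden in the main analysis; the sensitivity analysis shows how much that matters.
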